## 8.2 Statistical Analysis Plan

### 8.2.1 Responsibility for Analyses/In-House Blinding

The statistical analysis of the data obtained from this study will be the responsibility of the Clinical Biostatistics department of the SPONSOR.

This trial is being conducted as an open-label study, i.e., subjects, investigators, and SPONSOR personnel will be aware of subject treatment assignments after each subject is enrolled and treatment is assigned.

The Clinical Biostatistics department will generate the allocation schedule(s) for study treatment assignment.

### 8.2.2 Hypotheses/Estimation

Objectives and hypotheses of the study are stated in Section 3.0.

### 8.2.3 Analysis Endpoints

Efficacy and safety endpoints that will be evaluated for within-treatment differences are listed below, followed by the descriptions of the derivations of selected endpoints.

### **8.2.3.1 Efficacy/Immunogenicity/Pharmacokinetics Endpoints**

Efficacy and safety endpoints that will be evaluated for are listed below, followed by the descriptions of the derivations of selected endpoints.

#### **MDS (Cohort 1)**

The primary efficacy endpoint for the MDS cohort is ORR, defined as the proportion of subjects in the analysis population who have response according to the IWG 2006 criteria at any time during the study. Response for the primary analysis will be determined by the investigator.

Key secondary efficacy endpoints for the MDS cohort include:

- OS
- Bone Marrow Response based on IWG criteria for MDS (investigator-assessed)
- Hematologic improvement based on IWG criteria for MDS (investigator-assessed)
- Cytogenetic response based on IWG criteria for MDS (investigator-assessed)
- DOR
- Response by PD-L1 expression change before and after HMA treatment

Additional analyses of efficacy endpoints in MDS based on central review of bone marrow assessment may be conducted at the end of the trial and will be considered exploratory.

#### **MM (Cohort 2)**

The primary efficacy endpoint for the MM cohort is ORR, defined as the proportion of subjects in the analysis population who have response according to the IMWG criteria at any time during the study. Response for the primary analysis will be determined by the investigator.

Key secondary efficacy endpoints for the MM cohort include:

- CR + sCR rate based on IMWG criteria (investigator-assessed)
- TTP
- DOR
- PFS
- OS
- PD-L1 expression at baseline among responders/non-responders

### **Lymphoma – HL (Cohort 3)**

The primary efficacy endpoint for the HL cohort is CRR, defined as the proportion of subjects meeting the Revised Response Criteria for Malignant Lymphoma for a CR at any time during the study. Response for the primary analysis will be assessed by the investigator.

Key secondary endpoints in the HL cohort include:

- PFS
- OS
- ORR
- DOR
- PD-L1 expression at baseline among responders/non-responders

Additional analyses of HL efficacy endpoints based on central imaging assessment may be conducted at the end of the trial and will be considered exploratory.

### **Lymphoma –NHL monotherapy (Cohort 4)**

The primary efficacy endpoint for the NHL monotherapy cohort is ORR, defined as the proportion of subjects meeting the IWG criteria for an OR at any time during the study. Response for the primary analysis will be assessed by the investigator.

Key secondary endpoints in the NHL cohort include:

- PFS
- OS
- DOR
- PD-L1 expression at baseline among responders/non-responders

These endpoints will also be assessed separately for subjects with relapsed / refractory MLBCL (Cohort 4A), FL (Cohort 4C + FL subjects in Cohort 4B), DLBCL (Cohort 4D + DLBCL subjects in Cohort 4B), DLBCL combo (Cohort 5) and Other (non-FL and non-DLBCL Cohort 4B subjects).

Additional analyses of NHL monotherapy efficacy endpoints based on central imaging assessment may be conducted at the end of the trial and will be considered exploratory.

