#### **5.8 Subject Withdrawal/Discontinuation Criteria**

Subjects may withdraw consent at any time for any reason or be dropped from the trial at the discretion of the investigator should any untoward effect occur. In addition, a subject may be withdrawn by the investigator or the Sponsor if enrollment into the trial is inappropriate, the trial plan is violated, or for administrative and/or other safety reasons. Specific details regarding discontinuation or withdrawal procedures; including specific details regarding withdrawal from Future Biomedical Research, are provided in Section 7.1.4 – Other Procedures.

A subject must be discontinued from treatment (but may continue to be monitored in the trial) for any of the following reasons:

- The subject or legal representative (such as a parent or legal guardian) withdraws consent for treatment.
- Confirmed disease progression per respective response assessment criteria

Note: A subject may be granted an exception to continue on treatment with confirmed progression if clinically stable or clinically improved, please see Section 7.1.2.7.7.

- Unacceptable adverse experiences as described in Section 7.2.
- Any progression or recurrence of any malignancy, or any occurrence of another malignancy requires active treatment
- Intercurrent illness other than another malignancy as noted above that prevents further administration of treatment.
- Recurrent Grade 2 pneumonitis
- Investigator's decision to withdraw the subject
- The subject has a confirmed positive serum pregnancy test
- Noncompliance with trial treatment or procedure requirements

- The subject is lost to follow-up
- Administrative reasons

The End of Treatment and Follow-up visit procedures are listed in Section 6.0 (Protocol Flow Chart) and Section 7.1.5 (Visit Requirements). After the end of treatment, each subject will be followed for 30 days for AE monitoring (SAEs will be collected for 90 days after the end of treatment as described in Section 7.2.3.1). Subjects who discontinue for reasons other than PD will have post-treatment follow-up for disease status until disease progression, initiating a non-study cancer treatment, withdrawing consent or becoming lost to follow-up. After documented disease progression or the start of new antineoplastic therapy each subject will be followed by telephone for OS until death, withdrawal of consent, or the end of the study, whichever occurs first.

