#### **7.1.2.7.3 Disease Assessment of Immunotherapeutic Agents**

Immunotherapeutic agents, such as pembrolizumab, may produce antitumor effects by potentiating endogenous cancer-specific immune responses, which may be functionally anergic. The response patterns seen with such an approach may extend beyond the typical time course of responses seen with cytotoxic agents, and can manifest a clinical response after an initial increase in tumor burden or even the appearance of new lesions. Standard lymphoma disease response assessment criteria may not provide a comprehensive response assessment of immunotherapeutic agents such as pembrolizumab. Therefore, in the setting where a subject's lymphoma disease response assessment shows PD, trial treatment may be continued at the discretion of the principal investigator in a subject whose clinical condition is stable until repeat imaging performed to 6 weeks later confirms progression. However, imaging should occur at any time where there is clinical suspicion of progression. See Section 7.1.2.7.7 for additional information about the timing of the disease response assessment after PD.

**NOTE:** If a subject with confirmed progression according to response criteria for each cohort is clinically stable or clinically improved, an exception may be considered to continue treatment upon consultation with the Sponsor.

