### **7.1.2.7.7 Confirmation Assessments**

Because a subject treated with PD-1 inhibitors may have pseudoprogression of disease (there is progression per imaging, but the subject is clinically stable or improving), confirmation of progression should be conducted as follows:

After the first documentation of progression, it is at the discretion of the investigator to keep a clinically stable subject on trial treatment or to stop trial treatment until a disease response assessment performed 4-6 weeks later confirms progression.

Clinical stability may be defined as:

- 1) Absence of symptoms and signs indicating clinically significant progression of disease (including worsening of laboratory values) with the exception of M-protein elevation for the multiple myeloma cohort.
- 2) No decline in ECOG performance status.
- 3) Absence of rapid progression of disease or progressive tumor at critical anatomical sites (e.g., cord compression) requiring urgent medical intervention.

Subjects that are deemed clinically unstable are not required to have a repeat disease response assessment for confirmation.

If progression is confirmed, then the subject will be discontinued from trial treatment. If progression is not confirmed, then the subject should resume/continue trial treatment provided no other anti-tumor therapy (e.g., chemotherapy, radiation, etc.) has been administered.

Subjects should have their next disease response assessment as detailed in the Trial Flow Chart (see Section 6.0). When feasible, subjects should not be discontinued until progression is confirmed.

For subjects who have SD, partial response, or CR following the disease response assessment at Week 12, a confirmation assessment is not required. Disease assessments and imaging should continue per the regular frequency.

Subjects who have a CR for at least 18 months, irrespective of continued or discontinued trial treatment, may have subsequent imaging done every 6 months according to institutional standards until confirmed progression.

**NOTE:** If a subject with confirmed progression according to response criteria for each cohort is clinically stable or clinically improved, an exception may be considered to continue treatment upon consultation with the Sponsor.

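### The primary response window has no cut at confirmed progression, so a response recorded after it in a subject kept on treatment by exception counts toward the primary endpoint

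*Combined protocol and SAP*

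**What the plan says.** Section 8.2.3.1 gives each cohort's primary response the same open window. For Cohort 4 it is ORR, "defined as the proportion of subjects meeting the IWG criteria for an OR at any time during the study". For Cohort 3 it is the proportion meeting the lymphoma criteria "for a CR at any time during the study". Cohort 1 counts subjects "who have response according to the IWG 2006 criteria at any time during the study" and Cohort 2 those "who have response according to the IMWG criteria at any time during the study". Cohort 5 repeats the Cohort 4 wording, but Section 8.2.6 says it is not tested. Tables 15 and 17 add no end point to the window.

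Confirmed progression is a reason to discontinue treatment, but Section 5.8 adds a note: "A subject may be granted an exception to continue on treatment with confirmed progression if clinically stable or clinically improved". Sections 7.1.2.7.3 and 7.1.2.7.7 repeat the allowance, the latter saying that "an exception may be considered to continue treatment upon consultation with the Sponsor". Section 7.1.2.7.3 also explains that agents of this class "can manifest a clinical response after an initial increase in tumor burden or even the appearance of new lesions".

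Other sections limit data collection. Section 7.1.2.7.6 ends disease assessments at documented progression or new anticancer treatment. Section 7.1.5.3.2 ends efficacy follow-up at the same events. Section 7.1.5.3.3 moves subjects with confirmed progression, new therapy or a stem cell transplant into survival follow-up.

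**The concern.** Read together, these rules allow a subject to have confirmed progression, stay on treatment by exception, later meet the response criteria, and be counted as a primary responder. Nothing in the endpoint definition or the analysis tables says otherwise.

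Three features make this worth closing. The effect runs one way: an open window can add responders but never remove one. Response is investigator-assessed in an open-label trial, and the exception is agreed with the Sponsor, so the boundary is better fixed in advance than settled during programming. And Tables 15 and 17 analyse DOR in all responders, so such a subject would enter that analysis with a response dated after progression, with no rule for handling the dates.

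At stake is the pass or fail result of Cohorts 1 to 4, each judged against an exact threshold.

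**Working it through.** **Inputs.** From Sections 8.2.6 and 8.2.7: one-sided alpha of 0.05 per cohort. Cohort 4: n=78, null 25%, alternative 39%, threshold 27. Cohorts 1 and 3: n=25, null 10%, alternative 30%, threshold 6. Cohort 2: n=28, null 25%, alternative 50%, threshold 12.

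**Formula.** P(X ≥ r) = Σ over k from r to n of C(n,k) p^k (1−p)^(n−k).

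**Step 1: reproduce the design.** At the stated thresholds the exact alpha and power are:

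| Cohort | Rule | Alpha at the null | Power at the alternative |
|---|---|---|---|
| 4 | 27/78 | 0.037 | 0.818 |
| 1 and 3 | 6/25 | 0.033 | 0.807 |
| 2 | 12/28 | 0.029 | 0.828 |

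Each threshold is the smallest count with p below 0.05. The plan's statement of about 80% power is met or slightly exceeded.

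**Step 2: remove one responder at the threshold.** The p-value is P(X ≥ observed count) at the null.

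| Cohort | At threshold | One fewer |
|---|---|---|
| 4 | 27/78, p=0.037 | 26/78, p=0.061 |
| 1 and 3 | 6/25, p=0.033 | 5/25, p=0.098 |
| 2 | 12/28, p=0.029 | 11/28, p=0.068 |

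**Step 3: one certain post-progression responder.** That subject supplies one response. The other n−1 subjects, at the null rate, must supply r−1. The chance of declaring success is P(Y ≥ r−1) with Y binomial(n−1, null):

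- Cohort 4: P(Y ≥ 26 of 77 at 25%) = 0.053
- Cohorts 1 and 3: P(Y ≥ 5 of 24 at 10%) = 0.085
- Cohort 2: P(Y ≥ 11 of 27 at 25%) = 0.053

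**Step 4: a range of rates.** The documents give no rate of response after confirmed progression, so the fraction q below is an assumption. Suppose the response rate up to confirmed progression equals the null p0, and a fraction q of otherwise non-responding subjects respond afterwards. The counted rate is then p0 + (1−p0)q. For Cohort 4 with q=2% this is 0.25 + 0.75 × 0.02 = 0.265. The chance of reaching the threshold is:

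| q (assumed) | n=78 | n=25 | n=28 |
|---|---|---|---|
| 0.5% | 0.044 | 0.040 | 0.033 |
| 1% | 0.051 | 0.048 | 0.037 |
| 2% | 0.070 | 0.066 | 0.045 |
| 3% | 0.093 | 0.088 | 0.055 |

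**The case against.** The strongest reply is that the plan already limits most of this. Sections 7.1.2.7.6, 7.1.5.3.2 and 7.1.5.3.3 stop efficacy assessment at progression or new therapy, transplant included, and the myeloma criteria in Section 12.7.2 require response before any new therapy. A reader might infer that responses to later treatment inflate the endpoint; the documents do not support that. What remains is the subjects given the exception. Even for them, no section expressly schedules response assessment after confirmed progression; that they would be assessed while still treated is an inference. The lymphoma definition of PR in Section 12.7.3, which requires no new sites, makes some late responses harder to reach. These points narrow the gap. They are visit rules and response criteria, however, and none says that a later response is disregarded.

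Exposure is also uneven. The Document History says that Amendment 013-04 added the exception and that Cohorts 1 and 3 had by then completed enrollment. Only their subjects still on treatment could use it, so the n=25 figures carry the least exposure.

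Finally, counting late on-drug responses can be defended as a choice for this drug class. For the endpoint exactly as worded, the alpha values remain those in Step 1. The higher figures in Steps 3 and 4 treat the null as a statement about response up to confirmed progression. That stands, and it is why they are described here as the chance of declaring success and not as type I error.

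**Conclusion.** The point holds as a defect in the endpoint rule, limited to subjects treated past confirmed progression by exception. Following the plan exactly can count their later responses, and any effect favours success. Its size is unknown. One such subject matters only when the count is at the threshold, but there it decides the test. In Cohort 4 a single certain case moves the chance of success from 0.037 to 0.053, just above the nominal level. The n=25 figure of 0.085 is larger but applies where exposure is lowest. Cohort 2 stays below 0.05 up to an assumed 2% rate. Cohort 5 shares the wording but has no test.

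Three stronger readings are tempting, and the documents do not support them:

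- A reader might take 0.061 and 0.098 as false-positive rates with one such subject. They are p-values at a count one lower; the corresponding chances of success are 0.053 and 0.085.
- A reader might infer that the comparison with historical rates is broken. Table 18 says only that those rates are best objective response. Whether the cited studies counted post-progression responses cannot be seen.
- A reader might infer a conflict with the definitions of DOR and PFS. The plan states no PFS event rule and no DOR start date, so the dating problem is unresolved rather than contradictory. Cohort 1 has no PFS endpoint.

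**What to change.** In Section 8.2.3.1, define the primary response for Cohorts 1 to 5 as the best response from first dose up to the earlier of confirmed progression and the start of new anticancer therapy. State that responses after unconfirmed progression still count, which keeps the plan's allowance for pseudoprogression. State that responses after confirmed progression are reported separately as exploratory.

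The change is one sentence with two qualifiers. It leaves sample sizes, alpha, thresholds and patient management untouched and gives the DOR analysis a consistent set of responders. The cost is that ORR or CRR may come out slightly lower. Because the trial is open-label and Amendment 013-09 prepares its closure, the change should be dated and documented as a clarification of the endpoint, with the number of responses it reclassifies reported for each cohort.

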### **Lymphoma –NHL combination therapy (Cohort 5)**

The primary efficacy endpoint for the NHL combination therapy cohort is ORR, defined as the proportion of subjects meeting the IWG criteria for an OR at any time during the study. Response for the primary analysis will be assessed by the investigator.

Key secondary endpoints in the NHL cohort include:

- PFS
- OS
- DOR
- PD-L1 expression at baseline among responders/non-responders

Additional analyses of NHL combination therapy efficacy endpoints based on central imaging assessment may be conducted at the end of the trial and will be considered exploratory.

#### **8.2.3.2 Safety Endpoints**

A description of safety measures is provided in Section 4.2.3.1.

The primary safety endpoints are AEs graded using CTCAE (Version 4.0) criteria. Safety will be assessed by quantifying the toxicities and grades experienced by subjects who have received pembrolizumab (Cohorts 1 thru 4) or lenalidomide + pembrolizumab (Cohort 5), including SAEs and ECIs. Other safety endpoints include laboratory safety assessments, ECOG performance status, vital signs and physical examinations.

#### **8.2.4 Analysis Populations**

##### **8.2.4.1 Efficacy Analysis Populations**

The FAS population will serve as the primary population for the analysis of efficacy data in this study. The FAS population consists of all randomized subjects in each disease cohort who:

- Receive at least one dose of study treatment,
- Have a baseline disease assessment, and
- Have a post baseline disease assessment OR discontinue the trial due to PD/drug related AE

Supportive analyses will be conducted in the ITT population, defined as all randomized subjects.

For MDS cohort only, two additional subpopulations FAS/WHO-Classification and ITT/WHO-Classification will be used. These two populations have the same definition as above except for requiring the baseline disease assessment to satisfy WHO criteria.

Subjects will be included in the treatment group to which they are randomized for the analysis of efficacy data. Details on the approach to handling missing data are provided in Section 8.2.5 Statistical Methods.

#### **8.2.4.2 Safety Analysis Populations**

The All Subjects as Treated (ASaT) population will be used for the analysis of safety data in this study. The ASaT population consists of all allocated subjects who received at least one dose of study treatment.

At least one laboratory or vital sign measurement obtained subsequent to at least one dose of study treatment is required for inclusion in the analysis of each specific parameter. To assess change from baseline, a baseline measurement is also required.

Details on the approach to handling missing data for safety analyses are provided in Section 8.2.5 Statistical Methods.

#### **8.2.5 Statistical Methods**

Statistical testing and inference for safety analyses are described in 8.2.5.2. Efficacy results that will be considered to be statistically significant after consideration of the strategy for controlling the Type I error are described in Section 8.2.6, Multiplicity. Nominal p-values may be computed for other efficacy analyses as a measure of strength of association between the endpoint and the treatment effect rather than formal tests of hypotheses.

##### **8.2.5.1 Statistical Methods for Efficacy Analyses**

Efficacy will be evaluated separately in each disease cohort. For the primary efficacy endpoint, the point estimate, 90% CI, and p-value for testing primary endpoint rate is greater than the historical control for each cohort will be provided using exact binomial distribution. Subjects in the primary analysis population (FAS) without response data will be counted as non-responder.

Table 17 summarizes the key efficacy analyses.

Table 17 Analysis Strategy for Key Efficacy Variables

Endpoint/Variable (Description, Time Point)	Statistical Method	Analysis Population	Missing Data Approach
Primary 
 
1. MDS (Cohort 1): ORR based on IWG (2006) criteria for MDS (investigator-assessed)
 
2. MM (Cohort 2): ORR based on IMWG criteria (investigator-assessed)
 
3. HL (Cohort 3): Complete Remission Rate (CRR) based on IWG criteria (investigator-assessed)
 
4. NHL monotherapy (Cohort 4): ORR based on IWG criteria (investigator-assessed)
 
5. NHL combination therapy (Cohort 5): ORR based on IWG criteria (investigator-assessed)
 
	Exact test of binomial parameter (Cohorts 1 thru 4); Descriptive statistics (Cohort 5)	FAS (P) ITT (S)	Subjects with missing data are considered non-responders
Secondary binary endpoints 
 
1. MDS (Cohort 1):                     
 
a. ORR based on IWG (2006) criteria for MDS (investigator-assessed)
 
b. Bone marrow response by IWG criteria (investigator assessed)
 
c. Hematologic improvement by IWG criteria (investigator-assessed)
 
d. Cytogenetic response by IWG criteria (investigator assessed)
 
 
 
2. MM (Cohort 2):                     
 
a. CR + sCR by IMWG criteria (investigator assessed)
 
 
 
3. HL (Cohort 3):                     
 
a. ORR
 
 
 
4. NHL monotherapy (Cohort 4): none
 
5. NHL combination therapy (Cohort 5): none
 
	Exact test of binomial parameter	MDS ORR: FAS/WHO- Classification (P) ITT/WHO- Classification (S) All Others: FAS (P) ITT (S)	Subjects with missing data are considered non-responders

Endpoint/Variable (Description, Time Point)	Statistical Method	Analysis Population	Missing Data Approach
Secondary time-to-event endpoints 1. MDS (Cohort 1): a. OS b. DOR 2. MM (Cohort 2): a. TTP b. DOR c. PFS d. OS 3. HL (Cohort 3): a. PFS b. OS c. DOR 4. NHL monotherapy (Cohort 4): a. PFS b. OS c. DOR 5. NHL combination therapy (Cohort 5): a. PFS b. OS c. DOR	Summary statistics using Kaplan-Meier method	OS, TTP, PFS: FAS (P) ITT (S) DOR: all responders	Censored at last assessment
Secondary descriptive analyses Response by PD-L1 expression change before and after HMA treatment in each population separately: 1. MDS (Cohort 1) 2. MM (Cohort 2) 3. HL (Cohort 3) 4. NHL monotherapy (Cohort 4) 5. NHL combination therapy (Cohort 5)	Descriptive statistics	FAS (P) ITT (S)	

P=Primary approach; S=Supportive approach; FAS=Full Analysis Set; ITT=Intention to treat

In addition to the analyses specified above for overall cohort 4, separate efficacy analyses, descriptive in nature, will be performed with subjects with relapsed / refractory MLBCL (Cohort 4A), FL (Cohort 4C + FL subjects in Cohort 4B), DLBCL (Cohort 4D + DLBCL subjects in Cohort 4B), and Other (Cohort 4B excluding FL and DLBCL subjects).

The strategy to address multiplicity issues with regard to multiple efficacy endpoints is described in Section 8.2.6, Multiplicity and Section 8.2.9, Interim Analyses.

Exploratory objectives in each cohort will be evaluated using descriptive statistics.

